**Table 2: Analysis Visit Windows**

Visit Name	Visit Number	Target Start Day	Lower Limit	Upper Limit
Week 2	3	14	2	22
Week 4	4	28	23	42
Week 8	5	56	43	

**Table 3 Analysis Windows for Calculation of Average Weekly WI-NRS:**

Study Days for Calculation of average weekly WI-NRS	Week (Derived)
(-7, 1)*	Baseline
(2, 7)	Week 1
(8, 14)	Week 2
(15, 21)	Week 3

Study Days for Calculation of average weekly WI-NRS	Week (Derived)
(22, 28)	Week 4
(29, 35)	Week 5
(36, 42)	Week 6
(43, 49)	Week 7
(50, 56)	Week 8

\* Day 1 WI-NRS score will be used to calculate the “Baseline” only when it is collected before the application of the first study drug.

### 6.1.6. Pooling of Sites

Sites will be pooled for statistical analysis as follows. For analysis, sites should have a minimum of 10 randomized subjects (ITT population), with at least one subject in each treatment group.

The smallest sites within each country will be grouped sequentially in order of smallest to largest, restricting to those sites that did not meet the minimum enrollment of 10, until each pooled site has a minimum of 10 subjects with at least 1 subject in each treatment group in each strata combination.

As sensitivity analysis of different pooling strategy, sites that have randomized less than 50% of the number of randomized subjects at the site with the largest number of randomized subjects, those sites will be pooled within each country. The sensitivity analysis of pooling strategy will be applied for the primary endpoint only.

### 6.1.7. Derived Variables

- **Average weekly baseline WI-NRS** is defined as the average of all non-missing scores reported during the last 7 days prior to treatment if at least 4 of 7 evaluable daily WI-NRS questionnaires are available. Daily baseline WI-NRS is defined as the last non-missing assessment prior to the first study treatment.
- **IGA success** = IGA of “Clear” or “Almost Clear” plus at least 2-point improvement from baseline.
- **Study day** is calculated as:
  - observation date – first dose date + 1 if record is collected on or after first dose date
  - observation date – first dose date if record is collected prior to first dose date.

- **Compliance** = **number of applications** divided by the **expected number of IP applications** for each subject. Number of expected study treatment applications will be calculated as the sum of number of investigational product applications and number of doses missed. Compliance will be calculated using drug accountability data over the entire treatment period for each subject, up to treatment completion or discontinuation.
  - **Number of expected IP applications** = last treatment or missed dose date – first treatment date + 1.
  - **Number of IP applications** = number of expected IP applications – number of days with missed IP applications as collected in the CRF.
  - **Number of Days on IP** = last treatment date – first treatment date + 1.
- **Total Weight of IP Applied (g)** = dispensed can weight – returned can weight.
- **Average Daily Weight of IP Applied (g/day)** = total weight of IP applied/number of days on IP.
- **BMI (kg/m^2)** = (weight in kg)/[(height in cm/100)]. For Week 2, and 4, baseline height will be used to derive BMI. For Week 8, Week 8 height will be used to derive BMI since height is not collected at all visits.
- **BMI Categories:**
  - Underweight: BMI < 18.5
  - Normal: 18.5 ≤ BMI ≤ 24.9
  - Overweight: 25.0 ≤ BMI ≤ 29.9
  - Obese: BMI ≥ 30.0
- **Age Categories:**
  - 9 – 17 years
  - 18 – 64 years
  - ≥ 65 years
- **Duration (months) since diagnosis of seborrheic dermatitis** is derived as:
  - (Randomization date – diagnosis date)/30.4375
  - If day of diagnosis is not available, assume that diagnosis occurred on the 1st of the month.
- **WI-NRS 4-point Reduction** = achievement of at least 4-point reduction in average weekly WI-NRS pruritus score at Weeks 2, 4, and 8 compared to baseline, calculated only for subjects with a pruritus score of ≥ 4 at baseline (PRU4-ITT population).

- **Average Weekly WI-NRS Pruritus Score** will be calculated in a 7-day period, see table 3 for the analysis window. A minimum of 4 days of observations are needed to calculate average weekly WI-NRS.
- **DLQI Score** = sum of the 10 questions (individual questions scored as Very much=3, A lot=2, A little=1, Not at all=0, Not relevant=0, Question 7: Yes=3, No=0, with Not relevant recoded to 0; range for score 0 to 30). If 1 item is missing, it is scored as 0 for that item. If 2 or more items are missing, the score should not be calculated.
- **CDLQI Score** = sum of the 10 questions (individual questions scored as Very much=3, Quite a lot=2, Only a little=1, Not at all=0; Question 7: if the last week was school time, the question was scored as Very much=3, Quite a lot=2, Only a little=1, Not at all=0, with Prevented school recoded to 3, and if the last week was vacation, the standard responses apply; range for score 0 to 30). If 1 item is missing, that item is scored as 0. If 2 or more items are missing, the score should not be calculated.
- **PHQ-8** = sum of the 8 questions (individual questions scored as Not at all=0, Several days=1, More than half the days=2, and Nearly every day=3; range for score 0 to 24). If more than 1 item is missing the score should not be calculated. If 1 item is missing the score is calculated as (sum of answered items\*8)/number of answered items.
- **Modified PHQ-A** = sum of the 8 questions (individual questions scored as Not at all=0, Several days=1, More than half the days=2, and Nearly every day=3; range for score 0 to 24). If more than 1 item is missing the score should not be calculated. If 1 item is missing the score is calculated as (sum of answered items\*8)/number of answered items.
- **CDI-2** = total score is calculated as a sum of the 17 questions (individual questions scored as much or most of the time=3, often=2, some of the time=1, Not at all=0; range for score 0 to 51).
  - CDI-2 emotional problem scale is a sum of 9 questions (Q1, Q3-6, Q8, Q10 -12)
  - CDI-2 function problem scale is a sum of 8 questions (Q2, Q7, Q9, Q13-17)
- **Scalpdex Score Transformation** = Scalpdex is rated on a 1 to 5 scale which will be transformed to 0 to 100 Scale where 1=0; 2=25; 3=50; 4=75; 5=100. This transformed score is used to calculate scale scores.
  - **Emotions Scale** = average of (Q2, Q4, Q5, Q6, Q7, Q9, Q10, Q11, Q12, Q14, Q16, Q17, Q19, Q20, Q22) after transforming to 0 to 100 scale as mentioned above. Q refers to question number. Q19 will be reverse scored i.e., 1=100; 2=75; 3=50; 4=25; 5=0.
  - **Symptoms Scale** = average of (Q1, Q3, Q8) after transforming to 0 to 100 scale as mentioned above. Q refers to question number.

- **Functioning Scale** = average of (Q13, Q15, Q18, Q21, Q23) after transforming to 0 to 100 scale as mentioned above. Q refers to question number.
- **Scalpdex Total Score** = calculated as mean of all the 23 scalpdex questions using the transformed scale of 0 to 100. Q19 will be reverse scored i.e., 1=100; 2=75; 3=50; 4=25; 5=0 while calculating the mean. Q refers to question number.
- **Change from Baseline** = value at current time point – value at baseline.
- **TEAE** = any AE with onset date/time after the first application of IP.
- **C-SSRS Suicidal Ideation** = A “yes” answer at any time during treatment to any one of the five suicidal ideation questions (Categories 1-5: Wish to be Dead, Non-specific Active Suicidal Thoughts, Active Suicidal Ideation with Any Methods (Not Plan) without Intent to Act, Active Suicidal Ideation with Some Intent to Act, without Specific Plan Active Suicidal Ideation with Specific Plan and Intent).
- **C-SSRS Suicidal Behavior** = A “yes” answer at any time during treatment to any one of the five suicidal behavior questions (Categories 6-10: Preparatory Acts or Behavior, Aborted Attempt, Interrupted Attempt, Actual Attempt (non-fatal), Completed Suicide).
- **Trunk Involvement** = “Yes” if a subject has coverage area (trunk) greater than 0% as captured in the BSA page.

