#### **2.4.2. Risks and/or Benefits to Subjects**

Based on efficacy data from subjects randomized to active treatment group of the phase 2a study ARQ-154-203, including at Week 2, it is expected that subjects in the present study ARQ-154-304 will experience improvement in their seborrheic dermatitis. Subjects randomized to the vehicle treatment group may also see some improvement as the formulation of ARQ-154 may have a moisturizing effect.

The safety monitoring practices employed in this protocol (i.e., physical examinations, vital signs/weight, local skin toleration assessments, hematology, serum chemistry, urinalysis, PHQ-8/PHQ-A/CDI-2, C-SSRS and AE questioning) are adequate to protect the subjects' safety and should detect expected AEs. The lack of nausea and vomiting seen in ARQ-151 cream and ARQ-154 foam studies to date may be related to the lack of 'peak to trough'  $C_{max}$  variation, lower  $C_{max}$  values than observed following oral administration, or bypassing of the gastrointestinal tract with topical administration.

Oral roflumilast has now been used for almost a decade in the treatment of COPD exacerbations and its safety record has been well-documented. The known adverse effects of oral treatment in the COPD population (nausea, diarrhea, weight loss, psychiatric AEs) are readily monitored as specific in this protocol. The current protocol is designed to detect these adverse events and others should they occur, and provides guidance for management, as necessary, to ensure patient safety. Furthermore, the safety profiles of ARQ-151 and ARQ-154 at doses ranging from

0.15% to 0.5% in the preceding studies in seborrheic dermatitis and psoriasis suggests that ARQ-154 foam 0.3% will be similarly safe and well tolerated in the present study.

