### **9.4. Vital Signs**

Descriptive summaries of observed values and changes from baseline will be calculated for systolic blood pressure, diastolic blood pressure, heart rate, height, weight, body mass index and oral body temperature by treatment group and visit.

Changes in weight by treatment group will summarize the number of subjects who gain or lose  $\geq 5\%$  of their baseline body weight during the course of the study, as well as subjects who gain or lose  $\geq 10\%$  of their baseline body weight over the course of the study by treatment group and visit.

BMI is derived as specified in [Section 6.1.7](#). Shift tables (overall, subjects who indicated weight loss was intentional and subjects weight loss was not intentional at each visit) by treatment group for subjects who shift from their baseline BMI category (underweight, normal, overweight, obese) to a different BMI category throughout the course of the study will be provided by treatment group and visit.

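### The BMI-category shift tables apply fixed cut-offs from age 9, so 9-17-year-olds who start below 18.5 cannot show a downward shift

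*SAP*

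**What the plan says.** SAP 6.1.7 computes BMI as weight in kilograms over height in metres squared and sorts it into four categories. The lowest is "Underweight: BMI < 18.5", followed by "Normal: 18.5 ≤ BMI ≤ 24.9", "Overweight: 25.0 ≤ BMI ≤ 29.9" and an obese category from 30.0 upward. None of the four carries an age limit, although the same section goes on to define a 9-17 age group.

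The height used depends on the visit. For the interim visits: "For Week 2, and 4, baseline height will be used to derive BMI". For the last: "For Week 8, Week 8 height will be used to derive BMI since height is not collected at all visits". Protocol 5.1.5 has height measured at Baseline and Week 8 only.

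SAP 9.4 then plans shift tables, overall and by whether weight loss was intentional, "for subjects who shift from their baseline BMI category (underweight, normal, overweight, obese) to a different BMI category". SAP 14.1 lists them as tables 14.3.4.3 and 14.3.4.5 for the Safety population, with no age split in the titles. Enrolment starts at age 9 (Protocol 4.5.1).

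**The concern.** Protocol 2.4.2 names the known adverse effects of oral roflumilast as "nausea, diarrhea, weight loss, psychiatric AEs", and the SAP splits the BMI shift table by intentional and unintentional loss, so a reader will take it as a weight-loss display. A shift table can only show movement to a category that exists. A 9-17-year-old who starts below 18.5 is already at the bottom, so the table reports no change however much weight is lost. It also gives that subject an Underweight label from a cut-off that takes no account of age.

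A second, smaller matter is the change of height source at Week 8. The stated reason, that height is not taken at every visit, explains carrying baseline height to Weeks 2 and 4. It does not explain dropping it at Week 8, when it is still available. In an adult, a slightly different second reading changes BMI at that visit alone.

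**Working it through.** The documents give no figure for these tables, so there is nothing to reproduce. I apply the SAP's formula and cut-offs directly, reading the bounds as cuts at 18.5, 25 and 30. No worked value below falls between 24.9 and 25.0 or between 29.9 and 30.0, where the SAP's categories leave a gap.

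**1. Floor effect (SAP formula and cut-offs; body sizes are illustrations)**

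- Weight at which BMI reaches 18.5: 18.5 × height². At 135 cm, 33.7 kg; at 140 cm, 18.5 × 1.96 = 36.3 kg; at 150 cm, 41.6 kg.
- 140 cm, 33.0 kg: 33.0 / 1.96 = 16.8, Underweight. After a 10% loss, 29.7 / 1.96 = 15.2, still Underweight. No shift is counted.
- The result is the same at 135 cm and 30 kg (16.5) and at 150 cm and 40 kg (17.8) after a loss of 5%, 10% or 15%.
- The same 33.0 to 29.7 kg loss is exactly 10%, so it does enter the ≥10% weight-change count in SAP 9.4.

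**2. How many 9-17-year-olds start below 18.5**

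The documents give neither a planned number aged 9-17 nor their BMI distribution. Under an assumed normal distribution with SD 2.5 to 4.5, the share is 59-66% if mean BMI is 17.5, 34-41% if it is 19.5 and 12-25% if it is 21.5. The range shows only that the share cannot be fixed from the documents.

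**3. Height at Week 8, adults, weight unchanged**

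Week 8 BMI = baseline BMI × (baseline height / Week 8 height)².

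- Assumed 1 cm difference at 170 cm: (170/171)² = 0.9883, about 0.3 BMI units at BMI 25.
- 72.5 kg: 72.5 / 1.70² = 25.09 (Overweight); 72.5 / 1.71² = 24.79 (Normal). A downward shift with no weight change.
- Simulation assuming mean BMI 27 (SD 5) or 29 (SD 6.5), mean height 170 cm (SD 10) and independent reading error of SD 0.3 to 1.5 cm: 1.4% to 8.4% of adults change category at Week 8, about half of them downward. With baseline height, as at Weeks 2 and 4, the figure is 0%.

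**4. Height at Week 8, growing subjects**

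Assumed growth of 5 to 10 cm a year is 0.8 to 1.5 cm in 56 days. At 140 cm and constant weight this lowers BMI by 1.1% to 2.2%. That is real change, so a Week 8 height is reasonable under age 18.

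**The case against.** The strongest reply is that weight loss is well covered elsewhere. Protocol 6.2.3 plans the incidence of more than 5% weight loss or gain, and does not mention BMI categories. SAP 9.4 adds ≥5% and ≥10% counts and continuous summaries of weight and BMI by arm and visit. Table 14.3.4.4 splits weight change by intent. Subject-level monitoring also runs on percent weight loss (Protocol 4.8.6 and 5.1.5). This stands. A reader might infer from the floor effect that weight loss in children would go unreported; the documents do not support that.

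A reader might also infer that many children are affected. No number under 18 is planned or stated, and Phase 2a enrolled adults only (Protocol 2.3.1), so the number may be small.

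On height, using height and weight from the same visit is a defensible derivation, and any category table is sensitive near a boundary: at a fixed 170 cm, going from 72.5 to 71.9 kg (0.8%) takes BMI from 25.09 to 24.88 and also crosses. In a randomised, double-blind trial, reading error should be similar in both arms. This also stands. It rules out reading the Week 8 rule as an error or as a source of bias between treatments.

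The table shells are a separate document (SAP 15.1) and might split by age. The SAP text and table titles do not.

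**Conclusion.** The point holds, at limited size. For any 9-17-year-old with baseline BMI below 18.5, tables 14.3.4.3 and 14.3.4.5 assign a label from a cut-off without regard to age and cannot show a downward shift. That follows from the SAP's own definitions and needs no assumption. How many subjects it touches is unknown. The harm is confined to these descriptive tables: no inferential tests are planned on safety data (SAP 9), and the weight-based displays capture the loss.

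The Week 8 height rule is a free improvement rather than a correction. Its effect depends on an assumed reading error, arises at one visit, and adds similar noise to both arms.

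**What to change.** In SAP 6.1.7 and 9.4:

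- Limit the four-category BMI shift tables (14.3.4.3 and 14.3.4.5) to subjects aged 18 or over.
- For ages 9-17, show the already planned ≥5% and ≥10% weight-change counts as a separate age group. Age- and sex-specific BMI percentile categories are an alternative, provided the SAP names the reference.
- Optionally, for subjects aged 18 or over, use baseline height at Week 8 as at Weeks 2 and 4. Keep Week 8 height for subjects under 18.

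The cost is SAP wording, a small programming change and one small extra paediatric table. SAP version 3.0 was issued after database lock and unblinding, so the change must be labelled as such in the CSR, in line with SAP 10.1.

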### 5.2.6. Dermatology Life Quality Index (DLQI) and Children's Dermatology Life Quality Index (CDLQI)

The DLQI (ages 17+ years) and CDLQI (ages 9-16 years, inclusive) will be performed according to the Schedule of Visits and Assessments ([Section 1.3](#)). The DLQI/CDLQI is a simple, self-administered and user-friendly validated questionnaire. The DLQI/CDLQI is designed to measure the health-related quality of life of patients suffering from a skin disease. The DLQI/CDLQI consists of 10 questions concerning patients' perception of the impact of skin diseases on different aspects of their health-related quality of life over the last week.

The DLQI ([Appendix 8](#)) will be completed by subjects ages 17 years and older. The CDLQI ([Appendix 9](#)) will be completed by caregivers of subjects ages 9-16 years.

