## APPENDIX 8. DERMATOLOGY LIFE QUALITY INDEX (DLQI)

Site No: Date: **DLQI** Score:

Name: Diagnosis:

Address:

**The aim of this questionnaire is to measure how much your skin problem has affected your life OVER THE LAST WEEK. Please tick  one box for each question.**

1. Over the last week, how itchy, sore, painful or stinging has your skin been?	Very much 
	A lot 
	A little 
	Not at all 
2. Over the last week, how embarrassed or self conscious have you been because of your skin?	Very much 
	A lot 
	A little 
	Not at all 
3. Over the last week, how much has your skin interfered with you going shopping or looking after your home or garden ?	Very much 
	A lot 
	A little 
	Not at all 
	Not relevant 
4. Over the last week, how much has your skin influenced the clothes you wear?	Very much 
	A lot 
	A little 
	Not at all 
	Not relevant 
5. Over the last week, how much has your skin affected any social or leisure activities?	Very much 
	A lot 
	A little 
	Not at all 
	Not relevant 
6. Over the last week, how much has your skin made it difficult for you to do any sport ?	Very much 
	A lot 
	A little 
	Not at all 
	Not relevant 
7. Over the last week, has your skin prevented you from working or studying ?	Yes 
	No 
	Not relevant 

If "No", over the last week how much has your skin been a problem at work or studying?		A lot 
		A little 
		Not at all 
8.	Over the last week, how much has your skin created problems with your partner or any of your close friends or relatives ?	Very much 
		A lot 
		A little 

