### **2.2.1.3. Other Secondary Efficacy Endpoint(s)**

Other secondary efficacy endpoints of this study include the following:

- Change and percent change in Scalpdex total score from baseline at Weeks 2, 4, and 8.
- Achievement of an Overall Assessment of Erythema (0-3 scale) score of 0 at Weeks 2, and 4.
- Achievement of an Overall Assessment of Scaling (0-3 scale) score of 0 at Weeks 2, and 4.
- Change and percent change from baseline in Dermatology Life Quality Index (DLQI), Children’s DLQI (CDLQI) at Weeks 2, 4, and 8.
- Change and percent change from baseline in body surface area (BSA) affected at Weeks 2, 4, and 8.
- Change and percent change from baseline in Overall Assessment of Erythema score at Weeks 2, 4, and 8.
- Change and percent change from baseline in Overall Assessment of Scaling score at Weeks 2, 4, and 8.
- Achievement of an IGA score of ‘clear’ at Week 4.
- Achievement of an IGA score of ‘clear’ at Week 2.
- Achievement of daily WI-NRS score of 0 or 1.
- Change and percent change from average weekly baseline in WI-NRS

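### SAP 6.1.7 gives no score to the graded follow-up of DLQI Question 7, so as written the item can only be 0 or 3

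*SAP*

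**What the plan says.** SAP 6.1.7 defines the DLQI score as the sum of ten items. The general weights are "individual questions scored as Very much=3, A lot=2, A little=1, Not at all=0, Not relevant=0". Question 7 then gets its own rule, "Question 7: Yes=3, No=0, with Not relevant recoded to 0", and the total has "range for score 0 to 30". One missing item counts as 0; two or more missing items void the total.

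The form in Protocol Appendix 8 builds Question 7 in two parts. The stem begins "Over the last week, has your skin prevented you from" and concerns work or study, with the answers Yes, No and Not relevant. Those who answer No are then asked "over the last week how much has your skin been a problem at" work or study, with the answers A lot, A little and Not at all. Neither document scores that second part by name.

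The DLQI is completed by subjects aged 17 and older (Protocol 5.2.6). It feeds an other secondary endpoint in SAP 2.2.1.3, "Change and percent change from baseline in Dermatology Life Quality Index (DLQI), Children’s DLQI (CDLQI) at Weeks 2, 4, and 8", analysed by ANCOVA on observed data (SAP 8.3), and it appears among the baseline characteristics (SAP 7.3). SAP 8.1 keeps the other secondary endpoints out of the testing strategy.

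**The concern.** The item-specific rule assigns 0 to every No. A subject whose skin caused considerable trouble at work without preventing it therefore scores the same as a subject with no trouble at all, although the form separates the two. The middle grades of one item in ten disappear.

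Three outputs would be affected: the baseline DLQI, change from baseline, and percent change, whose denominator is the baseline total. The stated range gives no warning, because 0 to 30 is correct with or without the follow-up.

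**Working it through.** **Inputs.** The Question 7 rule, general weights and range are from SAP 6.1.7. The form is from Protocol Appendix 8. The number of items is from Protocol 5.2.6 ("The DLQI/CDLQI consists of 10 questions").

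**Step 1: reproduce the stated range.** Nine items with a maximum of 3 give 9 × 3 = 27. Adding 3 for Question 7 answered Yes gives 30, and the minimum is 0. The range reproduces, and it is the same if the follow-up is scored.

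**Step 2: score Question 7 both ways.** The graded column applies the SAP's own weights (A lot 2, A little 1, Not at all 0) to the follow-up.

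| Answer | SAP rule, literal | Graded | Points lost |
|---|---|---|---|
| Yes | 3 | 3 | 0 |
| No, A lot | 0 | 2 | 2 |
| No, A little | 0 | 1 | 1 |
| No, Not at all | 0 | 0 | 0 |
| Not relevant | 0 | 0 | 0 |

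The literal rule yields only 0 or 3; the graded rule yields 0, 1, 2 or 3. At a single visit the literal total is never too high.

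**Step 3: change from baseline.** Write L for the points lost at a visit. Then

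literal change − graded change = L(baseline) − L(follow-up).

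Each L lies between 0 and 2, so the error lies between −2 and +2. Two of the possible moves show both signs:

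- 'No, A lot' to 'No, Not at all': literal 0 − 0 = 0; graded 0 − 2 = −2. The improvement is missed.
- 'Yes' to 'No, A lot': literal 0 − 3 = −3; graded 2 − 3 = −1. The improvement is overstated by 2.

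Of the 5 × 5 = 25 baseline-to-follow-up pairs, 14 are mis-scored, 7 in each direction.

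**Step 4: treatment difference.** Randomisation makes the expected L(baseline) equal in the two arms. Before covariate adjustment, the expected error in the active-minus-vehicle difference in mean change is therefore

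mean L(follow-up, vehicle) − mean L(follow-up, active).

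If vehicle has more graded No answers at follow-up, the benefit is understated. If active has more, for instance because active subjects move from Yes to a graded No, it is overstated. The documents contain nothing that fixes the sign.

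**Step 5: effect on a visit mean (assumed frequencies).** No response frequencies are given, so these are illustrations only:

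- 10% with a graded No averaging 1 point: 0.10 × 1 = 0.1.
- 40% averaging 1.5 points: 0.40 × 1.5 = 0.6.
- Alternatively, 5% 'A lot' and 10% 'A little': 2 × 0.05 + 0.10 = 0.2; 20% and 30%: 2 × 0.20 + 0.30 = 0.7.

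**The case against.** The best defence is that the Question 7 clause only supplies codes for Yes and No, which the general list lacks, and that the follow-up answers keep their general weights, since A lot, A little and Not at all are all on that list. The clause also repeats the zero for Not relevant, so it need not be read as overriding everything before it. This reading is possible and fits the 0 to 30 range. But the SAP does not say to score the follow-up after a No; it says that No is 0. At the least, two programmers could derive different totals from the same form. The table shells are in a separate document (SAP 15.1), so how the item was actually programmed cannot be seen.

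A reader might infer that the rule pulls the treatment effect toward zero. The documents do not support that, because Step 3 shows errors of both signs. Nor does the rule understate change in everyone who clears: a subject who answered Yes at baseline and has no impairment at Week 8 changes by −3 under both rules.

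A reader might also contrast the children's version, where SAP 6.1.7 writes out the grades of Question 7 and ends with "Not at all=0, with Prevented school recoded to 3". This shows that the SAP spells out grades when it intends them, but it carries limited weight. That item is built differently, with school and holiday branches, and the two instruments are tabulated separately.

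The objection that little depends on this is fair: it concerns one item in ten, on an endpoint without formal testing.

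**Conclusion.** The rule is wrong as written, or at best incomplete. Read literally, it makes the DLQI total of a subject aged 17 or older 2 points too low after 'No, A lot' and 1 point too low after 'No, A little' at that visit, and it can put that item's change from baseline out by up to 2 points either way. These figures follow from the form and the SAP's weights alone.

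The effect on group means is not known. The 0.1–0.6 points for 10–40% of subjects, or 0.2–0.7 under the alternative split, rest entirely on assumed frequencies. The direction of any bias between arms cannot be determined. The consequence is confined to the DLQI summaries and the baseline table; the primary endpoint, the tested secondary endpoints and the safety analyses are untouched.

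**What to change.** In SAP 6.1.7, replace the Question 7 rule with: Question 7: Yes=3; if No, score the follow-up A lot=2, A little=1, Not at all=0; Not relevant=0. Count a No with a blank follow-up as a missing item under the existing rule. If it is the only missing item it still scores 0, as now; if a second item is missing, the total is void.

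Before rerunning anything, confirm that the follow-up answer was captured in the database and how the item was programmed. If the follow-up was already scored, only the SAP sentence needs correcting. If the literal rule was used, rerun Tables 14.2.6.1 and 14.2.6.2 and the baseline DLQI summary.

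The wording and code are cheap: one sentence and a short change to the derivation. There is also a reporting cost. The database was locked on 17 May 2022 and unblinded on 19 May 2022 (SAP 1), so the clinical study report must label the correction as made after unblinding, consistent with SAP 10.1. The rule is applied identically in both arms and uses weights already in the SAP, which makes it easy to justify.
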